8 RISKS AND BENEFITS

Affective disorders are associated with increased mortality in the form of increased suicide risk, but there is also increased mortality from other diseases such as cardiovascular diseases²⁰. The WHO considers depression to be the main cause of disability in the world, and as many as one in four Swedes are at risk of suffering from depression requiring treatment at some point in their lives²¹. Given the often-long duration of the disease, this means severe personal suffering and great costs for society. Affective disorders with anhedonia symptoms have been associated with more severe depressive symptoms, more relapses, and are also particularly strongly linked to suicide²². There is also a high risk that the symptoms of anhedonia will persist after the depression has otherwise improved, and there is currently no effective treatment that specifically targets anhedonia. There is therefore a great need in this population (affective disorder with anhedonia) to find effective treatment.

Treatment with pramipexole may cause dose-dependent side effects such as nausea, vomiting, orthostatic hypotension, headache and dizziness. In the elderly after long-term treatment, motor disorders, hallucinations, delusions, confusion, mania (rare) and disturbed impulse control may develop in severe cases, but this is less common²³. The risk of this is considered to be lower with shorter treatment times and with the use of prolonged-release drugs (as in the current study). Previous psychosis or impulse control disorder are examples of exclusion criteria in our study. In addition to unipolar depression and dysthymia, we will also include patients with bipolar disorder in the depressive phase in our study. A review of the literature has shown that the proportion of patients who make a switch from depression to a manic state during treatment with pramipexole is comparable (or even lower) to those who receive placebo²⁴. Unlike other dopamine receptor agonists, pramipexole can induce somnolence (especially at doses above 1.5 mg/day according to FASS) and in rare cases, patients have fallen asleep without warning²³. Therefore, patients affected by somnolence are instructed to refrain from driving and using machines until this side effect has been resolved. According to FASS, pramipexole is not contraindicated in any specific disease, in the treatment of Parkinson's disease the dose should be reduced in case of concomitant renal impairment (pramipexole is eliminated by the kidneys). Renal failure is another example of exclusion criterion in our study. Caution should also be exercised in patients with psychotic conditions and concomitant administration of antipsychotic medicinal products should be avoided.

Pramipexole is not indicated for the treatment of anhedonia symptoms and will be administered in this study mainly according to the Summary of Product Characteristics (SmPC) for the treatment of Parkinson's disease (maximum dose 4.5 mg of salt/day). This is also what has been done in previous clinical studies on depressed patients^{16,18,25}. However, in these studies, pramipexole doses above 4.5 mg have also been treated^{16,19}. As this increases the likelihood of neuropsychiatric side effects²³ and is not an approved dose range in Sweden, this does not occur in this study. The study population consists of adults who are able to give informed consent. The drug trial thus does not entail a major risk for research subjects, in which case an external safety committee is not considered justified. Adverse reactions are followed up with regular weekly contacts (bi-weekly telephone contact and bi-weekly physical visit) and are systematically recorded within the framework of the study.

The risk of severe adverse events is very small with dose ranges below 4.5 mg/day, which has been confirmed by several previous clinical studies with pramipexole in depressed patients¹⁹. Thus, the potential benefit of this pilot study, to demonstrate that this treatment is a feasible and tolerable intervention for depression with pronounced anhedonia symptoms, is greater than the risks for the included patients as it can lead to a successful treatment of the symptom of anhedonia in the future and increase the conditions for individual-based treatment.

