Pramipexole is a selective D3 receptor agonist which is primarily used as a treatment for Parkinson's disease (PS) and Willis-Ekbom disease (*Restless Legs syndrome*). Patients with PS often suffer from depression with anhedonia symptoms and it has been suggested that pramipexole has antidepressant effects in these patients by affecting dopaminergic neurotransmission¹⁵. Pramipexole has also been investigated in a small, randomized trial in unipolar and bipolar depression¹⁶⁻¹⁸. However, the clinical

effect has been too small to be widely justify treatment with pramipexole instead of usual antidepressants that have fewer side effects. However, in these studies, relatively low doses of pramipexole (an average of 1.0 mg) have been used when treating with pramipexole between 0.375 and 4.5 mg in Parkinson's disease. *The American Journal of Psychiatry* recently published a clinical review of patients with bipolar or unipolar therapy-refractory depression treated with pramipexole as adjunctive therapy. Interestingly, 76% reported an improvement that persisted up to 16 months after the end of treatment with an average dose of 2.5 mg pramipexole¹⁹. These results are promising because the patients in the study had a high degree of therapy resistance (several had not responded to ECT, for example), but the study was uncontrolled and took place within "clinical routine". Thus, well-controlled and systematic studies are needed before pramipexole can be recommended in the clinic.

In this pilot study, we want to test the efficacy and tolerability of pramipexole in the higher dose range (> 1.5 mg, max 4.5 mg salt) in patients with depression and with significant anhedonia symptoms despite usual treatment. The results of the study will form the basis for designing a larger placebo-controlled randomized trial. We also want to test the conditions for an fMRI scan before and after treatment to be able to demonstrate "*target engagement*". The aim of this is to eventually find biomarkers that can predict the treatment response of pramipexole.

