12 STUDY DESIGN

Visit	Screening	Baseline (last two weeks after Screening)	v1, v3, v5, v7, v9 +/- 2 days	V2, V4, V6, V8 +/- 2 day	v10 (termina tion) +/- 2 day	Follow-up during Tapering (v14) +/- 2 days
Informed consent	X					
Anamnesis	X					
MINI	X					
SUAS	X					
SHAPS		X		X	X	
MAP-SR		X		X	X	
GAD-7		X		X	X	
YMRS		X		X	X	
PGSI	X	X		X	X	
Insomnia Severity Index		X		X	X	
Fatigue Severity Scale		X		X	X	
Apathy Evaluation Scale		X		X	X	
Physical examination	X					
Blood pressure control	X			X	X	
Incl./exclusion criteria	X	X				
Blood tests β-hCG (if female of childbearing potential), eGFR, liver status, Hb.	X				X	
Inflammation tests (CRP, leukocytes, IL-6, TNF-alpha)		X			X	
fMRI (sub-study)		(X)			(X)	
Distribution of study product		X		X	(X)	
MADRS	X	X		X	X	
DARS	X	X		X	X	
Telephone contact			X			X
Incidents (AEs)			X	X	X	X

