12.5 DURING TREATMENT

Every two weeks during the study, the research subject is called to the research clinic to discuss up-titration and side effects as well as new assessment with MADRS and DARS. Blood pressure control is performed. A review of the dosing diary and assessment of compliance is sufficient for continued participation in the study (number of days of treatment completed, correct dosage, possible change of other antidepressant/mood stabilizing drugs). Every two weeks (between physical visits), telephone contact is made with the research subjects to check the up-titration status and any side effects. In case side effects develop between Visits/telephone contacts the research subject is asked to report this directly. The strategy if side effects occur is to go back to the last tolerable dose and wait seven days before re-attempting to increase (see section 13 for details).

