13 STUDY DRUG

13.1 INVESTIGATIONAL MEDICINAL PRODUCTS

In the study, the investigational medicine contains the active substance pramipexole. In Sweden, it was previously marketed under the name Sifrol but is now available in several generic versions. The dosage of pramipexole can be stated either as a base or as salt. In FASS, it is first and foremost the dosage as a base that is stated and the corresponding concentration in salt is given in parentheses. This protocol specifies dosage in salt form to be consistent with dosage indicated in the literature and abroad. In the diary and patient information for study participants, the dose is stated in base, as is stated on the medicine package and in the FASS.

Pramipexole is approved in the EU and is indicated as a symptomatic treatment of idiopathic Parkinson's disease, alone (without levodopa) or in combination with levodopa, in the maximum dose of 4.5 mg of salt. Pramipexole is also indicated as a symptomatic treatment of moderately to severely idiopathic restless legs syndrome in doses up to 0.75 mg of salt. Both apply to adults and not to children.

Pramipexole has a purely antidepressant effect (in addition to the effect on the underlying disease) in patients with Parkinson's disease, according to clinical studies. It has also been shown to reduce anhedonia symptoms in these patients³⁷. However, pramipexole has no approved indication for the treatment of mood disorders. In this study, the research subjects will reach a maximum dose of 4.5 mg of salt/day that is already approved for the treatment of Parkinson's disease.

Common Side Effects According to FASS (Indication Parkinson's Disease):

Very common (≥ 1/10): Somnolence, Dizziness, Dyskinesia and nausea.

Common (≥ 1/100, < 1/10): Insomnia, Hallucinations, Abnormal dreams, Confusion, Behavioral symptoms of disturbed impulse control and compulsive behavior, Headache, Visual impairment incl. diplopia, blurred vision and impaired visual acuity, Hypotension, Constipation, Vomiting, Fatigue, Peripheral oedema, Weight loss incl. decreased appetite.

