14.1 EFFICACY VARIABLES

Total score DARS (primary variable) and exploratory variables such as total score MADRS, SHAPS, MAP-SR, GAD-7, AES, *Fatigue Severity Scale* and *Insomnia Severity Index* gathered in a self-assessment questionnaire (validation of Swedish translation of DARS is in progress) at *screening-visit baseline*-visits and every other week for 10 weeks in connection with visit at the research clinic (a total of six occasions; MADRS and DARS on seven occasions).

Blood inflammation parameters (CRP, IL-6, TNF-alpha, and leukocytes) are collected at *baseline* and final visits. Other exploratory variables are collected during the fMRI examination.

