15.5 REGISTRATION OF INCIDENTS

At each contact once a week (every other week physical visit and every other week telephone contact), the research subject will be asked how he/she has been feeling since the previous contact. The research subjects are also informed to report any incident between these visits for discussion of dose changes, among other things. Incidents are recorded in the research subject's medical record and in the study's CRF. Registration of difficulty and relationship is only done in CRF. As a minimum, a description of the event (diagnosis or symptoms), start and stop, relationship, severity, and if it is considered serious, measures and outcome are recorded for each incident.

Incidents are followed from the start of treatment until four weeks after the end of visits. If the research subject wishes to continue with pramipexole after the end of the study, this is done in consultation with the research subject's PAL. In such cases, no dosage decrease takes place, but incidents are followed up for four weeks after the final visit via telephone contact until it is completed or after two attempts with contact without results.

All serious incidents will be followed until they are recovered or no longer necessary to be followed.

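### The instruction not to drive is worded for somnolence only, leaving out the sudden sleep named just before it, and no scheduled question is described as asking about either.

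*Combined protocol and SAP*

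**What the plan says.** Section 8 says that pramipexole can cause somnolence, especially above 1.5 mg/day, and that "in rare cases, patients have fallen asleep without warning". The next sentence draws the consequence: "Therefore, patients affected by somnolence are instructed to refrain from driving and using machines until this side effect has been resolved".

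Section 13.1 heads its side-effect list for the Parkinson's indication with "Somnolence, Dizziness, Dyskinesia and nausea", all classed as very common (at least 1 in 10). Section 7 says that the trial tests the "higher dose range (> 1.5 mg, max 4.5 mg salt"), which lies above the threshold flagged in section 8.

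Side effects are found in three ways:
- **Telephone, odd weeks (12.5):** "telephone contact is made with the research subjects to check the up-titration status and any side effects".
- **Every weekly contact (15.5):** "the research subject will be asked how he/she has been feeling since the previous contact".
- **Between contacts (12.5, 14.2.3, 15.5):** subjects are asked to report problems themselves.

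Section 8 describes this weekly follow-up as systematically recorded, section 14.2.3 repeats that adverse reactions are collected at visits and calls, and section 15.1 names somnolence as an example of an incident.

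**The concern.** The two hazards share a sentence and the rule follows with a word of consequence, yet the rule covers only one of them. Sudden sleep with no preceding sleepiness is the event for which a rule triggered by sleepiness gives least protection.

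The second part concerns how the events are asked about. Fatigue and sleep problems are themselves study symptoms (9.3), so a subject asked only how he or she has been feeling may put new sleepiness down to the depression and not mention it. At stake are the safety of a few subjects and the uniformity of the tolerability data by dose. Those data bear on the synopsis question about whether high-dose treatment is tolerable and on the design of the planned randomised trial.

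**Working it through.** The plan gives no figure on this point to reproduce. The check is of the text, with some arithmetic for scale.

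**1. Scope of the rule.** Section 8 names somnolence and sudden sleep; its instruction names somnolence only. The remaining sections contain no other rule on driving or machines. Sudden sleep is not named among the discontinuation criteria (11.2) or the exceptions that lead to tapering (13.3).

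**2. How each drug risk is asked about.**

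| Risk | Targeted tool | When |
|---|---|---|
| Impulse control (11.1.2, criterion 6; section 12 table) | PGSI plus specific questions on sex, shopping and food | Baseline and follow-up visits (PGSI also at screening) |
| Mania (13.3) | YMRS | Baseline, weeks 2, 4, 6, 8, 10 |
| Somnolence, sudden sleep | None described | General questions at each contact |

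The nearest scheduled scales are the "Insomnia Severity Index" and the Fatigue Severity Scale, described as measuring sleep problems and fatigue. Section 14.1 lists them as efficacy variables and gives the frequency: "a total of six occasions; MADRS and DARS on seven occasions". The six are baseline and v2, v4, v6, v8, v10, so neither scale is completed at a telephone contact. Their items are not reproduced in the documents, so it cannot be said whether they touch on daytime sleepiness.

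**3. How likely the rule is to be used.** Input: n = 15 (16.1). The 10% is the lower limit of the very common class in 13.1; carrying it over to this population is an assumption. Expected cases = n × p; chance of at least one = 1 − (1 − p)^n.

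- p = 5%: 0.75 expected; 1 − 0.95^15 = 0.537
- p = 10%: 1.5 expected; 1 − 0.90^15 = 0.794
- p = 20%: 3.0 expected; 1 − 0.80^15 = 0.965
- p = 10% among 10 completers: 1 − 0.90^10 = 0.651

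For sudden sleep the documents say only that it is rare. At assumed rates of 0.1%, 0.5% and 1%, the chance of at least one case among 15 is 1.5%, 7.2% and 14.0%. These are illustrations, not estimates.

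**4. Contacts above 1.5 mg.** Take contact n as the end of week n, and read the 1.5 mg in section 8 as salt, the convention stated in 13.1. On an uninterrupted schedule (13.3) the dose first exceeds 1.5 mg in week 4 (2.25 mg). Contacts v4 to v10 then fall above it: 7 of 10, covering 7 × 7 = 49 of 70 days. Three of the 7 (v5, v7, v9) are by telephone.

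One 7-day wait before the step to 2.25 mg leaves 6 contacts (3 by telephone), and two waits leave 5 (2 by telephone). A subject who stays at or below 1.5 mg has none. The visit table adds a telephone contact at v14. Under 15.5, subjects who continue pramipexole are followed for those four weeks without dose reduction, so some may still be at their final dose then.

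**The case against.** Five arguments count on the other side.

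- **The rule may need no staff detection.** Section 8 can be read as an advance warning that subjects apply themselves: if you become sleepy, do not drive. This stands. A reader might infer that the rule protects only as well as staff detect the symptom, but the text does not say so.
- **The wording that reaches patients is unseen.** Section 20.4 requires written and oral information on expected risks, and the patient information was not available. This stands. The inference that patients go unwarned is not supported.
- **Sudden sleep is part of the reason for the rule.** The link between the two sentences suggests that the authors meant to cover it. It would in any case be an incident under 15.1, could lead to a dose step-back under 13.3, and could lead the investigator to stop treatment under 11.2. This lowers the risk, but it also favours making the sentence say what was meant.
- **Monitoring is weekly and recorded.** This stands, and somnolence is not unmonitored. The remaining difference is between general and specific questions.
- **Sleepiness may already be captured before the first dose.** Incidents are followed only from the start of treatment, so a reader might infer that there is no pre-treatment information. Both scales are completed at baseline and their items are unseen, so that inference fails too.

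**Conclusion.** The point holds as a minor one. The section 8 rule omits one of the two hazards that lead to it, and no other section of the documents supplies the missing clause. Separately, two events that bear on driving are sought by general questions only, as far as the protocol describes, while impulse control and mania have targeted tools.

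The 79% (54% to 96% for assumed rates of 5% to 20%) means that the rule will probably be used at least once. It would be wrong to read it as the chance of a missed case: the rule already covers somnolence, and the documents give no basis for estimating how many cases general questions would miss. The contact counts describe exposure above 1.5 mg in the same limited sense. The conclusion rests on the protocol text alone, since neither the patient information nor the CRF's incident pages could be read. No efficacy endpoint, sample size or test is affected.

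**What to change.** 1. **Section 8.** State that a subject with somnolence, or with any episode of falling asleep without warning, refrains from driving and using machines until it has resolved.
2. **Sections 12.3, 12.5, 12.6 and 15.5, and the visit table.** Add two fixed yes/no questions, one on daytime sleepiness and one on sudden sleep. Ask them at baseline, at each of the 10 existing weekly contacts and at the v14 telephone contact, and record the current dose with each answer. Assess a yes during treatment or follow-up as an incident under 15.1. The driving instruction follows if somnolence or sudden sleep is confirmed.
3. **Section 16.3.** Report the answers descriptively by dose, with baseline beside them. The sudden-sleep question serves safety; 15 subjects cannot give a rate.

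The cost is one extended sentence and two CRF lines at 1 + 10 + 1 = 12 contacts: 12 × 2 = 24 answers per subject, and at most 24 × 15 = 360 in all. No visit is added. The drawback is that prompted counts run higher than unprompted ones and are less comparable with studies that used open questions; the baseline answers partly offset this.

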9 RESEARCH QUESTIONS

The aim of the project is to treat patients with mood disorders and anhedonia symptoms with pramipexole as an adjunct to usual treatment. This open-label pilot study is intended as *proof of concept* (PoC) and we hope to obtain preliminary data that can form the basis for a larger, more definitive, placebo-controlled study. We evaluate dosing ranges to achieve sufficient treatment effect without obtaining intolerable side effects. According to the literature, this should be an average dose of about 2.5 mg/day but is expected to vary between individuals. For example, it is known that D3 receptors vary with age (fewer at older age) and that older individuals tolerate and need higher dosages to achieve treatment effect. Several previous clinical studies with pramipexole have, like this study, used variable and flexible dosage.

Blood samples are taken before and after treatment for analysis of inflammatory markers in order to investigate whether these can predict treatment response. We also want to investigate how the function of the brain's reward system is linked to anhedonia and treatment response. To this end, an fMRI (MID-task: test of the reward system) is planned to be performed before and after treatment with pramipexole (not mandatory to participate in the treatment study). This data will also form the basis for future follow-up studies aimed at better understanding the neurobiology behind anhedonia and to make prediction analyses of the treatment effect of pramipexole.

9.1 PRIMARY RESEARCH QUESTION AND VARIABLE

Primary question: Change in anhedonia symptoms after ten weeks of treatment with pramipexole at the highest possible dose (without intolerable side effects, max 4.5 mg).

Primary variable: Dimensional Anhedonia Rating Scale (*DARS*) score at *baseline* and week 10 of pramipexole treatment.

9.2 SPECIFIC RESEARCH QUESTIONS AND VARIABLES

Secondary question: Change in depression symptoms after ten weeks of treatment with pramipexole? How many respond to pramipexole (*responders*) and how many reach remission?

Secondary variable: Total-score MADRS. Response = reduction in MADRS by over 50%, remission = MADRS <= 10 after study end.

9.3 EXPLORATORY RESEARCH QUESTIONS AND VARIABLES

Exploratory question: What dosage of pramipexole has an effect on anhedonia symptoms without causing intolerable side effects? Is there a connection between anhedonia symptoms and systemic inflammation in the body? Does pramipexole treatment affect other symptoms associated with depression such as fatigue, anxiety, lethargy, and difficulty sleeping? Correlates estimation of anhedonia symptoms with DARS with estimation of secondary anhedonia scales (SHAPS, MAP-SR). Increases Task in the brain's reward system after treatment with pramipexole and is this linked to clinical efficacy? **Explorative variable:** We will evaluate optimal dosing intervals, i.e. lowest and highest final dose where the patient had clinical efficacy and at the same time no non-tolerable side effects. We will also evaluate the number of *dropouts*, change in blood levels of inflammatory markers, as well as change in anxiety symptoms (GAD-7), fatigue (Fatigue Severity Scale), sleep

problems (Insomnia Severity Index), and apathy (AES). Correlation between Snaith–Hamilton Pleasure Scale (SHAPS) and Motivation and Pleasure Scale (MAP-SR) total score compared to DARS total score. Difference in BOLD signal in ventral striatum (NAc) during *monetary incentive delay task* before and after pramipexole treatment.

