Study population	
Inclusion (not exhaustive list): Age between 18 years and 75 years Diagnosis of unipolar depressive episode, bipolar disorder in depressive phase or dysthymia. Moderate to severe depression but with pronounced symptoms of anhedonia. To be able to participate, you must have an ongoing stable treatment with at least an antidepressant/mood stabilizer for at least 4 weeks.
 
Exclusion (not exhaustive list): Current pregnancy, breastfeeding or planned pregnancy. High suicidal. Substance abuse. Psychotic disorder. Compulsory treatment (LPT). Impulse control disorder. Diagnosis of moderate/severe renal failure or severe cardiovascular disease. Recently started psychotherapy. Ongoing ECT treatment.

Study design	
Proof of concept study, in which fifteen research subjects are included and receive study treatment (no placebo or control group occurs). All included research subjects will also be asked to participate in the substudy for fMRI examination before and after 10 weeks of treatment with pramipexole.

Timetable	
Study start: 1 September 2019 Study end: 1 December 2020.

Statistical considerations	
The objective of the study is to demonstrate feasibility (proof of concept) and we hope to generate preliminary data that will form the basis for a larger, definitive, randomized controlled trial. Specifically, we are interested in investigating: i) can we pick up a signal in our material that pramipexole has an anti-anhedonic effect in this study population, (ii) if the treatment doses we propose are reasonable: treatment effect versus side effects, iii) what the distribution looks like for DARS before and after treatment in order to optimize future dimension calculations.

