Method description	
Patients will be recruited from outpatient psychiatric clinics or inpatient wards. Those who meet the inclusion criteria and none of the exclusion criteria will, at the screening visit, undergo a baseline assessment including self-report rating scales and blood sampling for inflammatory markers (CRP, IL-6, TNF-alpha, white blood cells).
 
Participants who also consent to the substudy will undergo an fMRI examination of the brain's reward system (MID task). Thereafter, study treatment will begin according to the protocol, with dose escalation once weekly until treatment effect, maximum dose, or intolerable side effects occur. In the event of intolerable side effects, the participant will return to the last tolerable dose. A new attempt at dose escalation may be made after seven days, up to a maximum of two attempts. If serious adverse events occur, the medication will be tapered off.
 
After ten weeks of pramipexole treatment, a final visit will be conducted including new assessment with self-rating scales and blood samples as at baseline visits (including new fMRI examination for those participating in the substudy).

Financing	
The study is financed by funds from ALF, the Söderström-Königska Foundation, SUS Donations and Foundation and the Royal Physiographic Society in Lund.

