The tablets are usually taken at night if the research subject does not have sleep problems. If non-tolerable side effects occur in connection with an increase in dose, the research subject is encouraged to notify this and return to the dosage that did not cause side effects. After that, wait another seven days before a new attempt at dose increase occurs. This is done on a maximum of two occasions before giving up attempts to reach a higher dosage (treatment continues with the lower dosage if possible). An exception to this strategy is if the study participant experiences side effects in the form of impulse control disorder (e.g. pathological gambling addiction or compulsive buying behavior), manic state, or symptoms of heart failure. If such a situation arise, pramipexole will be tapered off and discontinued. Study participants will be assessed with YMRS at baseline, week 2, week 4, week 6, week 8 as well as at week 10 to evaluate any manic symptoms.

The total duration of treatment is ten weeks before an evaluation of efficacy is made and a decision is made on continued treatment or discontinuation (referral is sent to PAL, which is responsible for continued treatment with pramipexole). If the research subject during the study shows a 50% decrease on MADRS or a 50% increase on DARS (=response), further dose increase is stopped, and the research subject then remains on this dose for the rest of the study. Control of *compliance* This is done by asking the research subject to bring the remaining tablets (and dosage diary) to the evaluation visits every two weeks for control counting of the number of tablets.

Pramipexole treatment must not be stopped abruptly due to the risk of dopamine *agonist withdrawal syndrome* (DAWS) with symptoms such as depression, anhedonia, apathy, anxiety, sleep disturbances, and others. The study participant is carefully informed about this. If discontinuation of the drug becomes necessary, this will be done gradually as instructed in FASS: The pramipexole dose is gradually reduced by 0.75 mg of salt per day until the daily dose is reduced to 0.75 mg of salt. The dose should then be reduced by 0.375 mg of salt per day. The patient is instructed to report any withdrawal side effects and then the dose reduction can be individualized to counter them.

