16.3 STATISTICAL ANALYSIS OF PRIMARY, SECONDARY AND EXPLORATORY VARIABLES

All statistical analysis is performed using the IBM SPSS Statistics v24 software. Paired T-test (2-tailed) is used to analyze the difference in DARS scores between *baseline* and after ten weeks of treatment with pramipexole (primary variable). Normal distribution is expected based on previous studies. Descriptive analysis is performed by response (reduction by at least 50% in MADRS score), remission (MADRS ≤ 10 at study end) of depression symptoms (secondary variable), and number of *dropouts*. Descriptive analysis, mean and *range*, is performed on the dosage of pramipexole at the end of the visit. Of the exploratory variables, similar *paired* T-tests (or equivalent non-parametric method if necessary) are used for the analysis of difference in total scores MADRS, SHAPS, MAP-SR, AES, GAD-7, Fatigue Severity Scale and Insomnia Severity Index.

Analyses may also be made on imputed datasets. If values are missing from the measurements over time, they will be replaced with the means of adjacent values before and after the missing value or with the last observation.

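### The exploratory optimal dosing interval in 9.3 is built from final doses that the stop-at-response rule in 13.3 partly determines, so one chance responder at week 2 can set its lower limit at 0.75 mg

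*Combined protocol and SAP*

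**What the plan says.** Section 9.3 asks which dosage affects anhedonia without intolerable side effects. It answers with an interval, the "lowest and highest final dose where the patient had clinical efficacy and at the same time no non-tolerable side effects". The section does not say what counts as clinical efficacy.

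Section 13.3 contains the nearest definition, as a titration rule: if a participant "shows a 50% decrease on MADRS or a 50% increase on DARS (=response), further dose increase is stopped". The dose reached at that point is held until treatment ends. The synopsis has the same design, "with dose escalation once weekly until treatment effect, maximum dose, or intolerable side effects occur". The scales that trigger the rule are rated at the clinic visits: "Every two weeks during the study, the research subject is called to the research clinic to discuss up-titration" (section 12.5). No confirming rating is required before the dose is held.

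The synopsis makes dose one of three specific aims, asking "if the treatment doses we propose are reasonable: treatment effect versus side effects". Section 16.3 plans a mean and range, which "is performed on the dosage of pramipexole at the end of the visit". That summary covers everyone and is not limited to participants with efficacy.

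**The concern.** A final dose can be read as a dose that worked only if it was not itself chosen by the outcome. Here it was. A participant who crosses the 50% threshold is held where they are; one who does not goes on to the maximum or to intolerance. Among those stopped by response, final dose is the scheduled dose at the visit where the threshold was first met. Dose and weeks on study rise together, so improvement with time, regression to the mean or expectancy looks the same as response to a dose. No control group or randomised dose separates them.

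The summary then takes the smallest and largest of these values, so one person can fix each end. The lower end is the more exposed, because the first rated visit falls at 0.75 mg and section 7 describes the range under test as above 1.5 mg. A pilot meant to prepare a placebo-controlled trial could hand over a dose range that partly restates its own titration schedule.

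**Working it through.** **The plan's figure.** The documents give no figure for the interval, so there is none to reproduce. Section 16.1 supplies two usable inputs: DARS SD 13.73 and r = 0.5. The implied SD of change is 13.73 × √(2 × (1 − 0.5)) = 13.73.

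**Doses at the rated visits (13.3).** Week 2: 0.75 mg. Week 4: 2.25 mg. Week 6: 3 + 0.75 = 3.75 mg. Week 8: 4.5 mg, reached in week 7. On schedule, a response stop can only give one of these four values. If the ±2-day window put the week 2 visit just after the next step, the held dose would be 1.5 mg, still not above 1.5 mg.

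**Chance response at one rating.** Assume an inert drug and a DARS change that is normal with mean 0 and SD S. From baseline b, a 50% rise has probability 1 − Φ(0.5b/S).
- b = 20, S = 13.73: 10/13.73 = 0.73, probability 0.23.
- b = 26, S = 13.73: 13/13.73 = 0.95, probability 0.17.
- b = 20, S = 10: probability 0.16.
- b = 20, S = 6: probability 0.05.

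**Chance that the lower limit is 0.75 mg.** Entry requires DARS below 27 (11.1.1), but the baseline distribution is not given, so I assume it uniform on 10–26 or on 20–26. Let p be the chance of response at week 2, and q the chance of response at both week 2 and week 10, with correlation 0.5 between visits. If efficacy must be present at week 10, the lower limit is 0.75 mg with probability 1 − (1 − q)^n.

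| SD of change | p; q (baseline 10–26) | n = 15 | n = 10 | p; q (baseline 20–26) | n = 10 |
|---|---|---|---|---|---|
| 6 | 8.1%; 2.72% | 34% | 24% | 2.9%; 0.58% | 6% |
| 9 | 16.7%; 7.00% | 66% | 52% | 10.2%; 3.35% | 29% |
| 12 | 23.1%; 10.94% | 82% | 69% | 17.0%; 6.90% | 51% |
| 13.73 | 25.9%; 12.86% | 87% | 75% | 20.2%; 8.84% | 60% |

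For example, 1 − (1 − 0.1286)^15 = 1 − 0.127 = 0.87. Simulating the stop rule visit by visit agrees to about one point: 34%, 67%, 82% and 88% for n = 15, and 6% to 61% for the last column. The ranges quoted elsewhere in this note are the simulated ones.

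**If response at any visit counts.** The probability becomes 1 − (1 − p)^n: 72%, 93%, 98% and 99% for n = 15 with baseline 10–26, and 25%, 66%, 84% and 89% for n = 10 with baseline 20–26.

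**Sensitivity.**
- If correlation decays by a factor of 0.5 per visit step, the n = 15, baseline 10–26 figures under the week 10 reading fall to 16%, 43%, 62% and 69%.
- A second simulation added the MADRS route to response. It assumed baseline MADRS about 28 and DARS about 21, change SDs of 6–8 and 6–13.73, visit autocorrelation 0.6, dose-independent improvement of 0–30% by week 10, and all doses tolerated. Under the week 10 reading the lower limit was 0.75 mg in 10–91% of trials (n = 15) or 7–80% (n = 10).
- In that simulation, under the any-visit reading with n = 15, the upper limit was 4.5 mg in 63–99% of trials. Over all settings, mean final dose among any-visit responders was 2.4–3.4 mg. Section 9 expects about 2.5 mg/day, so an inert drug could seem to confirm it.

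**The case against.** The strongest reply is about weight. The variable is exploratory and descriptive, in an uncontrolled proof-of-concept study of 15 people. No test, decision rule or dose selection hangs on the interval, and with so few participants every dose can be listed. That stands, and it limits the consequence to the dose conclusions carried into the later trial.

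The second reply is that the size depends on inputs the documents do not supply. That stands too. A 50% rise is easy from a low baseline (5 points from 10). The power calculation plans for at least 10 completers, not 15. The SD of 13.73 comes from depressed patients in the scale's development and becomes a change SD only through r = 0.5. Entry truncated below 27 may narrow the spread, and at that SD about 11% of simulated week 2 scores fall below zero.

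Third, treating clinical efficacy as response is a reading of an undefined term, and someone held at a low dose by intolerance could also set the lower end. Both are true. Neither makes the interval interpretable as optimal.

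A reader might also infer that section 16.3 plans this analysis. It does not: its mean and range are unrestricted and serve as a description of exposure.

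**Conclusion.** The point holds as a matter of structure. Under 13.3 the final dose of a participant stopped by response reflects when the threshold was first met, so the lowest and highest such doses do not identify an optimal interval.

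A reader might go further and say that chance responders will set the lower limit even if the drug does nothing. The documents do not support that certainty. It is a probability, about 34–88% or about 6–61% under the two sets of assumptions above, and the plan contains nothing that would narrow it. In the most favourable case (10 completers, baseline 20–26, SD 6, response still present at week 10) it is unlikely.

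Nor does this reach the primary DARS comparison, or show that the titration rule is wrong. The fault lies in what is inferred from final dose. Because dose reasonableness is a stated aim and the correction is cheap, it should be made.

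**What to change.** Leave titration as it is and change the reporting.

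- In 9.3, stop presenting the lowest-to-highest final dose among those with efficacy as an optimal interval. If the term clinical efficacy is kept for any other purpose, define it.
- In 16.3, keep the mean and range of final dose as a description of exposure. Add a table of final dose by the reason escalation ended (response, maximum dose, intolerance, withdrawal), and the proportion tolerating each dose step among those who reached it.
- State that the pilot informs tolerability by dose, not the relation between dose and efficacy.

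Reporting the dose at the first rating that met response would not help: the dose is held from then on, so barring a later reduction it is the final dose again.

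The cost is one CRF item (why escalation ended), one table, and a more modest claim about dose.
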